9.5.3 Expected power

The expected power to rule out a target threshold RR of 2.5 was computed at the meta-analysis level based on the expected number of exposed pregnancies in the data sources. There are three data sources (USA (Carelon Research), USA (DAPI) and France) that contribute to the meta-analysis for the MCM outcome, irrespective of anifrolumab exposure proportion (see Table 10 and Table 11). These three data sources also contribute to the meta-analysis of the select pregnancy loss outcomes. Additionally, Denmark contributes to the meta-analysis of the select pregnancy loss outcomes if the assumption of 10% for anifrolumab exposure is used. For select pregnancy loss outcomes, the expected power to rule out an RR of 2.5 was superior to 99% in all scenarios

(Table 13). For MCM outcomes, the expected power to rule out an RR of 2.5 was equal or superior to 69% assuming 5% of exposure to anifrolumab among pregnant SLE women, and equal or superior to 96% assuming 10% of exposure to anifrolumab among pregnant SLE women (Table 13).

Table 13: Expected power in the meta-analysis of select pregnancy loss and MCM with 5% and 10% of all pregnancies in women with moderate-to-severe SLE exposed to anifrolumab.

Final study reporting year	Data sources included in the meta-analysis of select pregnancy loss	Expected power for the meta-analysis of select pregnancy loss outcomes		Data sources included in the meta-analysis of MCM	Expected power for the meta-analysis of MCM	
		1:2 matching ratio	1:3 matching ratio		1:2 matching ratio	1:3 matching ratio
5% exposure to anifrolumab						
2032	USA (Carelon Research) USA (DAPI) France	>99%	>99%	USA (Carelon Research) USA (DAPI) France	69%	72%
2034 (study extended by 2 years)	USA (Carelon Research) USA (DAPI) France	>99%	>99%	USA (Carelon Research) USA (DAPI) France	80%	84%
10% exposure to anifrolumab						
2032	USA (Carelon Research) USA (DAPI) Denmark France	>99%	>99%	USA (Carelon Research) USA (DAPI) France	96%	98%
2034 (study extended by 2 years)	USA (Carelon Research) USA (DAPI) Denmark France Germany (RHEKISS)	>99%	>99%	USA (Carelon Research) USA (DAPI) France	>99%	>99%

9.6 Data management

IQVIA (who will perform the PASS on behalf of AstraZeneca) will take responsibility for application for the study permits, obtaining necessary approvals (ethical or otherwise), and access to the study data. Generally, the data will be stored and analysed in accordance with local policy.

All data used in this study will be in the form of electronic records, and the data holders collect and manage data according to their own standards.

The identification of the study population will be conducted by the individual data source holders according to the specifications given in Section 9.2. After the identification of the study population from different data sources, study data from each data source will be extracted. The data extraction will be conducted by the individual data source holders.

After data is extracted, the data holders will make data accessible to IQVIA, according to data permits in each specific country. The details of the data permits will be confirmed only once the data permits are granted. If the data permits allow, individual-level data will be accessed by IQVIA. However, individual-level data from some of the data holders (e.g., Carelon Research (USA)) cannot be accessed by IQVIA but will be managed and analysed by the data provider (e.g., HealthCore). All individual-level data accessible to IQVIA will have original personal identifiers replaced with a study identification number (SID). Thus, IQVIA will not have access to data that allow individuals to be directly identified.

IQVIA will adhere to all local and regional laws on data protection and privacy. IQVIA will also adhere to IQVIA standard operating procedures. Data management for this study will be conducted using standard IQVIA processes. IQVIA will maintain appropriate data storage, including periodic backup of files and archiving procedures and will comply with procedures that include checking electronic files, maintaining security and data confidentiality, following analyses plans, and performing quality checks for all programmes.

The general principles for data management and statistical analyses will be described in detail in the SAP. Therein all data checks to be performed on completeness, plausibility and consistency of collected data will be described in detail with identification of data discrepancies. IQVIA will perform all data management and statistical analyses using statistical software (Statistical Analysis System (115) version 9.4 or later, STATA or R [version 3.5.0 or later]). The data providers conducting the data management and statistical analysis for the study will store the datasets and analytic programmes according to the data provider's procedures.

Full audit trail starting from raw data obtained from register holders and ending to statistical tables and graphs in reports will be maintained. Source code of data management and data analyses will be kept for inspection for 5 years after publication of results. The study may be inspected by the AstraZeneca's independent representative(s), scientific committee, or by the competent authorities.

9.7 Data Analysis

All data analysis will be performed separately for each data source on the study population as defined in Section 9.2.2. The study population selection process will be reported using a STROBE

(STrengthening the Reporting of OBservational studies in Epidemiology) diagram that shows cohort and sub-population exclusions step by step, as defined in Section 9.2.2.

All study results will be presented separately for each data source in the study reports, as appropriate when data become available. The full study reports for all data sources, including all descriptive, comparative, exploratory, and sensitivity analyses, as well as the meta-analysis results will be provided in the final report. The study reporting is described in detail in Section 6.

A full description of the analytical approach will be developed and described in the SAP. Also details on data derivations, category definitions, analyses, and presentation of the study results will be provided in SAP. The SAP will be finalised prior to the conduct of the study analyses.

In this study, the missing data will be reported as part of descriptive analysis (see Section 9.7.1). Methods commonly used in non-interventional studies for handling missing data, such as imputation, complete case analysis or indicator for missing values, will be considered (35). The SAP will describe the full details on handling missing data that will include the methods for identifying where missing data methods should be applied, the techniques for identifying the type of missing information and the appropriate imputation methods to be used, if any.

The small number masking rules define the lower limit for the number of units that can be reported in a table. The small number masking rules vary by data sources. For example, Denmark and Finland have a limit of 5, USA (Carelon Research) has a limit of 10 and France has a limit of 11. The small number masking rules of the data sources will be considered when presenting the study results for descriptive and comparative analysis. If the small number masking rules apply, only the comparative analysis results for the relevant study outcome (and no descriptive analysis results for the relevant study outcome) will be provided to avoid inadvertent unmasking of small numbers.

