9.5.1.1 Assumptions used for the sample size and power calculations

To estimate the number of anifrolumab exposed SLE pregnancies and the expected number of primary study outcome events in data sources that would be eligible for the analysis in this study, the following assumptions were used:

- **A prevalence of 7% for MCM outcome.** Prevalence of MCM in pregnancies in women with moderate-to-severe SLE was estimated based on a literature search. Among moderate/severe SLE patients exposed to belimumab, birth defect prevalence estimates of 5.6% to 21.7% were observed in post hoc summary of clinical studies and a prospective

pregnancy registry, respectively (86) A prevalence of 6.4% of congenital malformations was observed in renal SLE pregnancies (51) These proxy estimates of MCM in moderate-to-severe SLE align with the observed population based prevalence estimates ranging from 7.4% to 13.6% (114) among women diagnosed with SLE (117).

- **A prevalence of 20% for the composite of select pregnancy loss outcomes (composite of spontaneous abortion and stillbirth).** Prevalence of the composite outcome of select pregnancy loss (spontaneous abortion and stillbirth) in moderate-to-severe SLE pregnancies ranged from 15.3% to 30% (51, 81, 86). For the individual outcomes, the prevalence estimates ranged from 1.8% to 3.7% for stillbirths (51, 103, 120), and the prevalence estimate was 16% (12.1% to 19.9%) for spontaneous abortions (103). Based on the intended objective to evaluate embryo-foetal loss, a composite outcome of spontaneous abortion and stillbirth has been used.
- **Proportion of SLE pregnancies occurring in women with moderate-to-severe disease of 50%.** There is limited information on the proportion of SLE pregnancies that occur in women with moderate-to-severe disease. The proportion of moderate-to-severe disease at the time of diagnosis among the general SLE population is estimated to be 50% (66, 80). Literature regarding medication patterns for SLE pregnant women suggests that 40-45% use immunosuppressors and/or biologics, which may be a proxy indicator of moderate/severe disease (12, 67). Thus, in this study, an assumption of 50% was used.

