For the comparison of the study sub-cohorts exposed to anifrolumab and unexposed to anifrolumab within the study cohorts (as defined in Section 9.2.2), the association metrics of RRs will be estimated. The RRs will be estimated if there is at least one outcome event observed per exposure group. Both crude and adjusted RRs will be reported and estimated for each relevant study outcome. The crude and adjusted RRs will be estimated before and after PS adjustment, respectively. The adjusted RRs will be reported only if PS adjustment is suitable for the data. The statistical model to be used for the estimation of the crude and adjusted RRs will be the log-binomial regression or the robust, modified Poisson regression as seen appropriate for the study data (13, 18). If covariate balance is not achieved through PS adjustment, additional adjustment by using unbalanced covariates in the outcome regression model will be considered. Additionally, any other potential covariates (or risk factors) that are not included in the PS model but are hypothesised to be associated with the study outcomes may be used as covariates for the statistical models. Further details on the statistical models will be provided in the SAP.

Meta-analysis

In addition to data source level analyses, results will be combined in a meta-analysis. Meta-analysis will be performed only for the adjusted RR estimates of the primary study objectives (MCM and selected pregnancy loss outcomes). The meta-analysis will be performed using effect size estimates from all study countries for which the adjusted RR were estimated.

Prior to conducting the meta-analyses, heterogeneity across the study countries will be assessed using:

- Cochran's Q test (significance level: 0.1). Q is calculated as the weighted sum of squared differences between individual studies and the pooled value across studies.
- The I^2 statistic (0% to 40%: might not be important; 30% to 60%: may represent moderate heterogeneity; 50% to 90%: may represent substantial heterogeneity; 75% to 100%: considerable heterogeneity). I^2 is calculated as follows:

$$I^2 = \left(\frac{Q - df}{Q} \right) \times 100\%$$

where Q is Cochran's statistic and 'df' is its degrees of freedom. The I^2 is a statistic that estimates the percentage of variance in effects attributable to study heterogeneity rather than sampling error.

- The τ^2 statistic

Considerable heterogeneity would indicate that the study results should be interpreted as inconclusive.

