- For some data sources, there are reporting restrictions based on the overall number of events. For example, in Danish data sources, when the outcome for a specific analysis, has less than 5 cases/observations, the specific result and other potentially related results cannot be reported. This is because of the potential of patient identification. This may be a potential limitation for analyses that require stratifications, such as the exploratory analysis to investigate the risk of CM by target body system organ class or the risk of select pregnancy loss outcomes (composite of spontaneous abortion and stillbirth) by different pregnancy trimesters. In this instances, minimum and maximum values cannot be reported.

Also, some study analysis limitations must be acknowledged.

- Confounding by indication is common in comparative observational studies, and as the prescription of anifrolumab will depend on the assessment of the severity or activity of the disease, confounding by indication may occur. However, in this study, mitigation strategies, such as selection of only moderate/severe SLE cases has been planned to minimise the presence of confounding by indication. Furthermore, PS methods will be applied to minimise the potential for confounding due to differences in baseline characteristics between the exposed and unexposed groups.

- Regarding SLE SOC, the recordings of exposure based on prescription or dispensation alone do not guarantee that the patient ingested or injected the medication; the recordings of prescriptions are an expression of the treating physician's recommendation of the drug, and the prescriptions dispensed at community pharmacies and insurance claims registrations are an expression of the patients' intention to follow the recommendation from the physician.

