10. PROTECTION OF HUMAN SUBJECTS

This non-interventional study involves the use of pseudonymised electronic healthcare records and does not affect the treatment of the patients. The study is conducted in accordance with the ENCePP Code of Conduct (34), the Guidelines for GPP (37), the Declaration of Helsinki and its amendments, and any applicable national guidelines, laws and regulations. AstraZeneca, the Contract Research Organisation (CRO), other participating entities and individuals acting on their behalf commit to adhere to the rules of the ENCePP Code of Conduct in their entirety.

The CRO will receive pseudonymised data including dummy SIDs only. AstraZeneca will not have access to the patient-level data at any time of the study.

Due to data protection restrictions in the study countries (e.g., Denmark and Finland), the cells in tables with few observations need to be masked. Thus, cells in tables must include a minimum of 5 observations and summary statistics can only be calculated if a minimum of 5 observations are used. In addition, minimum and maximum values may not be reported due to the protection of subjects' privacy in specific study countries (e.g., Denmark, Finland).

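### The small-number masking rule would probably withhold the exposed MCM risk (primary Objective 1) in all four sources with a stated limit, and no pooled risk replaces it

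*Protocol*

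**What the plan says.** Section 9.7 lists the limits as examples: "Denmark and Finland have a limit of 5, USA (Carelon Research) has a limit of 10 and France has a limit of 11". No limit is given for DAPI or RHEKISS. Where a limit applies, "only the comparative analysis results for the relevant study outcome (and no descriptive analysis results for the relevant study outcome) will be provided".

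Objective 1 is primary. Section 9.7.2 answers it with the crude and adjusted cumulative incidence of MCM, separately for exposed and comparator offspring, in each data source. Section 9.7.1 then restricts pooling: "Meta-analysis will be performed only for the adjusted RR estimates of the primary study objectives". No absolute risk is pooled.

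Two other sections also describe masking. Section 9.9, with Danish data and fewer than 5 cases as its example, says "the specific result and other potentially related results cannot be reported". It adds: "This may be a potential limitation for analyses that require stratifications", and names organ class and trimester as the cases in point. Section 10, with Denmark and Finland as examples, says that "summary statistics can only be calculated if a minimum of 5 observations are used".

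**The concern.** The protocol's own event forecasts for MCM lie below its own masking limits. For 2032, Table 11 (10% uptake) expects 7 exposed MCM events in Carelon, 8 in France and 0 in Denmark and Finland. Table 10 (5% uptake) expects 3, 4, 0 and 0. The rule deletes every descriptive result for the outcome, so a low exposed count would also remove the comparator risk and the time-to-ascertainment description.

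Two things are at stake. A primary objective would mostly go unanswered where a limit is stated. And a Carelon or France risk would appear only when the count happens to be high, which is an upward selection in a safety study. Section 9.9 does not warn of either, because it treats masking as a problem for stratified and exploratory analyses.

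In addition, section 9.7 keeps the RR when counts are masked, while section 9.9 would withhold related results. An RR computed from masked counts is such a result.

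**Working it through.** **Inputs.** MCM risk: "A prevalence of 7% for MCM outcome" (9.5.1.1). Pregnancy-loss risk: "A prevalence of 20% for the composite of select pregnancy loss outcomes" (same section). Exposed numbers come from 9.5.1.2 and Tables 10 and 11. Limits come from 9.7, reading a limit L as masking any count below L, including zero.

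**Reproducing the plan's figures (10% uptake, 2032).** Expected events = n × 0.07:
- Carelon 102 × 0.07 = 7.14
- DAPI 114 × 0.07 = 7.98
- France 116 × 0.07 = 8.12
- Denmark 8 × 0.07 = 0.56
- Finland 6 × 0.07 = 0.42

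Rounded down, these are 7, 7, 8, 0 and 0, as in Table 11. The chance of at least one event, 1 − 0.93^n, is 44% for Denmark and 35% for Finland, also as tabulated.

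**Probability of masking.** P(X < L) with X ~ Binomial(n, 0.07):

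| Source (limit) | 10%, 2032 | 5%, 2032 | 10%, 2034 |
|---|---|---|---|
| Carelon (10) | n=102: 82% | n=51: 99.7% | n=124: 63% |
| France (11) | n=116: 81% | n=58: 99.8% | n=150: 52% |
| Denmark (5) | n=8: >99.9% | n=4: 100% | n=10: >99.9% |
| Finland (5) | n=6: >99.9% | n=3: 100% | n=8: >99.9% |

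At 5% uptake Denmark and Finland have fewer than 5 exposed pregnancies in total, so the limit cannot be reached. If zero counts could be shown, masking at 10% uptake in 2032 would fall to 44% in Denmark and 35% in Finland; Carelon and France would not change to the precision shown.

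**Selection among released risks (10%, 2032).** E[X/n | X ≥ L]:
- Carelon: 10.9%, released with probability 1 − 0.823 = 18%
- France: 10.6%, released with probability 1 − 0.811 = 19%

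Against a true 7% these are 10.9/7 = 1.56 and 10.6/7 = 1.51 times too high.

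**What pooling would give.**
- 10% uptake: 102 + 114 + 116 = 332 exposed, 332 × 0.07 = 23.2 events, P(fewer than 11) = 0.1%.
- 5% uptake: 51 + 56 + 58 = 165 exposed, 165 × 0.07 = 11.6 events, P(fewer than 11) = 39%.

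**The conflict between sections.** Under section 9.7 the Danish RR survives masking; under section 9.9 it may not. Section 9.5.3 leaves Denmark out of the pooled MCM analysis but includes it for pregnancy loss at 10% uptake. There 11 × 0.20 = 2.2 events are expected and P(X < 5) = 95%. Simulating the plan's fixed-effect analysis with and without Denmark gives pregnancy-loss power above 99% both times.

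**The case against.** The limits are imposed by data holders, and section 9.6 says permit details are known only once permits are granted. Section 9.7 keeps the RR, so Objective 2 stands. The masking probabilities depend on uptake and reporting year, and the protocol provides for interim review, extension and additional sources. An unmasked risk from 8 Danish or 6 Finnish pregnancies would tell little. DAPI, with about 8 expected events and no stated limit, would on the text report its risk whatever its size. A bound such as <10 of 102 is not shown to be permitted and, printed beside an RR and its CI, might help someone recover the count.

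Most of this stands and limits the point. It does not remove it. The choice to delete every descriptive result, and the absence of a pooled risk, are the protocol's own. Even with the 2034 extension at 10% uptake, masking is more likely than not in both Carelon and France.

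A reader might also infer that sections 9.9 and 10 remove the Carelon and France MCM RRs, so that the stated MCM power of 96% (1:2) and 98% (1:3) is lost. The documents do not support this. Section 9.9 illustrates its rule only for Danish data below 5 cases, and section 10 only for Denmark and Finland; neither country is expected in the pooled MCM analysis. Applying that consequence at limits of 10 and 11 builds a rule that the text never states. Section 10 also counts observations, and an RR from 102 or 116 exposed pregnancies uses far more than 5.

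**Conclusion.** The point holds for the descriptive primary objective. In all four sources with a stated limit, the exposed MCM risk would probably be withheld: 82% in Carelon, 81% in France and over 99.9% in Denmark and Finland at 10% uptake, and over 99.7% in Carelon and France at 5%. Nothing pooled takes its place. Carelon and France risks that are released at 10% uptake overstate a true 7% by about half. This rests on the protocol's 7% risk, its exposed numbers and the reading of the limits given above. It cannot be extended to every source, because DAPI and RHEKISS have no stated limit.

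The disagreement between sections 9.7 and 9.9 is real but small in effect: at most the Danish pregnancy-loss RR is in doubt, and pooled power stays above 99% without it. No loss of MCM power is implied. Severity: should-fix.

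**What to change.** 1. In sections 9.7.1 and 9.7.2, add a pooled MCM risk with 95% CI for the exposed and comparator groups as the Objective 1 result, subject to each holder's permit. At 10% uptake about 23 exposed events across Carelon, DAPI and France clear every stated limit. At 5% about 12 are expected, which may still fall below 11, so the text should say what is reported in that case.
2. Align sections 9.7, 9.9 and 10 on whether a source-level RR and its standard error may go to the meta-analysis when the underlying counts are masked.
3. In section 9.9, name Objective 1 as affected, and state that source-level MCM risks released only above a masking limit are selected upward.

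Bounded reporting (such as <10 of 102) should be used only where the holder allows it. The cost is one small extra analysis, edits to three sections and a permit clause per holder.

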9.7.1 Methods

Propensity score methodology for confounding

Methods based on propensity score (PS) are frequently used in non-interventional studies to control for confounding when estimating treatment effects (6). PS methods allow for control of measured confounding in treatment effects when the measured confounders related with the treatment are correctly modelled in the PS (107). In non-interventional studies, the widely used methods that employ PS methods in adjusting for confounders include PS matching and PS weighting using inverse probability treatment weighting (IPTW). In this study, the average treatment effect in the treated (ATT) is the estimand of interest. To estimate ATT using PS matching, each patient within the study treatment is matched either to one (i.e. 1:1 matching) or more (i.e. 1:n matching) patients who have the same or a similar PS value (65). In PS matching, the patients in the study treatment cohort who do not have a close enough match in the comparator treatment cohort need to be excluded from the analysis (65). To estimate ATT using IPTW, each subject in the study treatment cohort has a weight of one and each subject in the comparator treatment cohort has a weight of the odds of receiving the study treatment i.e. $PS/(1-PS)$ (6). This

weighting approach is also known as standardised mortality ratio weighting, and it creates a pseudo-population of the comparator treatment cohort that has the same covariate distribution as the study treatment cohort (107). The PS weighting approach excludes patients from the original study population when there are non-overlapping PS values in the study cohorts (65). The PS weighting with IPTW is vulnerable to patients with extreme PS weights, but truncation methods will be used in this study if PS weighting is used and extreme PS weights are observed (19, 65).

In this study, PS matching will be considered as the preferable PS adjustment method. PS matching will be used if it does not significantly reduce the sample size, otherwise PS weighting will be used. In PS matching, if there are many more patients in the comparator treatment cohort than in the study treatment cohort, each patient in the anifrolumab exposed cohort may be matched to more than one patient (e.g., 1:2 or 1:3 matching) to increase statistical power.

The PS adjustment will be performed separately within each data source and for each study cohort that is derived from the study populations as defined in Section 9.2.2. In this study, the PS will be obtained using a logistic regression model or another modelling method (e.g., gradient boosting) as seen appropriate for the data. For the PS model, all the potential confounders listed in Table 7 Section 9.3.3 will be considered for inclusion. All these potential confounders will be estimated before or at conception, or before or at the start of exposure, as seen relevant for the confounder (see Section 9.3.3). Specifically, each single component of the SLE severity and activity algorithms (described in Section 9.3.3) will be considered for inclusion in the PS model. The maximum number of confounders to be included in the PS model will be one fifth of the minimum between the number of exposed or unexposed patients in the study cohort (as defined in Section 9.2.2) (17). The PS adjustment will be performed only if the PS model can be fit on the available data and if the PS model fit is reasonable (17). If PS adjustment is not suitable for the data, no adjusted estimates of the study outcomes will be provided in the study results. Further details on the PS modelling will be provided in the SAP.

To check the overlap and similarity of the PS distributions between the study sub-cohorts (exposed to anifrolumab and unexposed to anifrolumab, as defined in Section 9.2.2), the distribution of the propensity scores in the study sub-cohorts will be examined (49). To evaluate the balance of covariates within the study cohorts, the characteristics of the study sub-cohorts (exposed to anifrolumab and unexposed to anifrolumab, as defined in Section 9.2.2) will be tabulated before and after application of PS adjustment. Covariate balance will be assessed by examining the distribution of variables in the study sub-cohorts using summary statistics, and by estimating standardised differences for each variable between the study sub-cohorts (exposed to anifrolumab and unexposed to anifrolumab, as defined in Section 9.2.2). No statistical tests are planned for this comparison, but variables with standardised differences above 0.1 will be further evaluated and may lead to a re-evaluation of the PS model. Further details will be provided in the SAP.

Descriptive analysis

In the descriptive analysis, the total number of patients at risk and the number of events for each study outcome in the study sub-cohorts (exposed to anifrolumab and unexposed to anifrolumab as defined in Section 9.2.2) will be tabulated before and after application of PS adjustment, if suitable for the data. The measures of study outcomes will be estimated before and after application of PS adjustment (if suitable for the data) to obtain crude and adjusted estimates, respectively. The measures of study outcomes, with associated 95% CIs, will be estimated for the study sub-cohorts exposed to anifrolumab and unexposed to anifrolumab as defined in Section 9.2.2. In this study, cumulative incidence (i.e. incidence proportion) by exposure status to anifrolumab during pregnancy will be assessed for the following study outcomes: MCM (objective 1 & 15), select pregnancy loss outcomes (composite of spontaneous abortion and stillbirth) (objective 3 & 13), mCM (objective 6), adverse pregnancy outcomes (objective 8), adverse birth outcomes (objective 10), and adverse outcome related to infant growth up to one year of age (objective 12).

Additionally, the description of the time from birth to MCM ascertainment will be conducted in live and non-live offspring from women who had moderate/severe SLE and were exposed or unexposed to anifrolumab during the first trimester of pregnancy. The time to MCM ascertainment will be calculated from birth and up to 1 year after birth. The time to MCM ascertainment will be estimated both before and after application of PS adjustment (if suitable for the data) to obtain crude and adjusted estimates, respectively. Kaplan-Meier curves (and their 95% CIs) will be used for characterising the time from birth to MCM ascertainment. Together with the Kaplan-Meier curves, the number of patients at risk at appropriate time intervals (e.g., 7 days or as seen appropriate for the study), and the median (with 95% CI) for the time from birth to MCM ascertainment will be reported.

For study objective 5 (secondary objective), descriptive analysis will be conducted to describe the demographic and clinical characteristics of the live and non-live offspring and their mothers (defined in Section 9.3.3) in the study sub-cohorts exposed to anifrolumab and unexposed to anifrolumab as defined in Section 9.2.2. For the descriptive analysis of continuous variables, the number of observations, number of missing values, mean, standard deviation, median, lower (1st) and upper (3rd) quartiles, as well as 5th and 95th percentiles will be presented. For categorical variables, the numbers and percentages of observations for each of the categories and numbers and percentages of missing values will be presented in descriptive analysis.

Additionally, descriptive summaries of the number and proportion of mothers who received anifrolumab in the preconception period will be reported. These descriptive summaries will include the total number of anifrolumab administrations per mother in the preconception period summarized as a continuous variable, and the timing of anifrolumab administrations in the preconception period summarized as the number and proportion of mothers who received anifrolumab in pre-specified time intervals (e.g., within 4 weeks before LMP, within 4-8 weeks before LMP etc., or as seen appropriate for the study data). In addition, the descriptive summaries will include the timing of the last anifrolumab administration per mother. The description of

anifrolumab administrations may also be extended to mothers who received anifrolumab during pregnancy, if appropriate for the study. Further details will be provided in the SAP.

Comparative analysis

For the comparison of the study sub-cohorts exposed to anifrolumab and unexposed to anifrolumab within the study cohorts (as defined in Section 9.2.2), the association metrics of RRs will be estimated. The RRs will be estimated if there is at least one outcome event observed per exposure group. Both crude and adjusted RRs will be reported and estimated for each relevant study outcome. The crude and adjusted RRs will be estimated before and after PS adjustment, respectively. The adjusted RRs will be reported only if PS adjustment is suitable for the data. The statistical model to be used for the estimation of the crude and adjusted RRs will be the log-binomial regression or the robust, modified Poisson regression as seen appropriate for the study data (13, 18). If covariate balance is not achieved through PS adjustment, additional adjustment by using unbalanced covariates in the outcome regression model will be considered. Additionally, any other potential covariates (or risk factors) that are not included in the PS model but are hypothesised to be associated with the study outcomes may be used as covariates for the statistical models. Further details on the statistical models will be provided in the SAP.

Meta-analysis

In addition to data source level analyses, results will be combined in a meta-analysis. Meta-analysis will be performed only for the adjusted RR estimates of the primary study objectives (MCM and selected pregnancy loss outcomes). The meta-analysis will be performed using effect size estimates from all study countries for which the adjusted RR were estimated.

Prior to conducting the meta-analyses, heterogeneity across the study countries will be assessed using:

- Cochran's Q test (significance level: 0.1). Q is calculated as the weighted sum of squared differences between individual studies and the pooled value across studies.
- The I^2 statistic (0% to 40%: might not be important; 30% to 60%: may represent moderate heterogeneity; 50% to 90%: may represent substantial heterogeneity; 75% to 100%: considerable heterogeneity). I^2 is calculated as follows:

$$I^2 = \left(\frac{Q - df}{Q} \right) \times 100\%$$

where Q is Cochran's statistic and 'df' is its degrees of freedom. The I^2 is a statistic that estimates the percentage of variance in effects attributable to study heterogeneity rather than sampling error.

- The τ^2 statistic

Considerable heterogeneity would indicate that the study results should be interpreted as inconclusive.

Results of the meta-analysis will be derived using a fixed-effect model since it is expected that the effect is the same in all study countries. A random-effects model can be conducted as a sensitivity analysis if substantial heterogeneity is observed. Data source-specific results and the overall combined estimate will be presented in forest plots including effect size and 95% CI for each study country included in the analysis. Further details will be presented in the SAP.

